T2: Two-week intervention. Following baseline assessments, participants will be randomly assigned to the mindfulness intervention or coping control intervention condition. Participants will complete one 20-minute audio-guided lesson each day, plus receive 3 brief text-based practice prompts daily at random times. The interventions were developed by [name] and [name] and are matched on attentional demand, lesson length and structure, and voice. Interventions will be delivered via smartphone app that securely tracks participant activity, including timestamps at lesson and practice prompt start/completion and daily survey responses (stress assessments pre- and post-lesson, pre- and post-practice prompt, and each evening; practice prompt receptivity). This data will be integrated with phone sensor and wearable data to inform future JIT intervention tailoring. Staff will check in with participants on intervention days 3, 9, and 14 to provide support and monitor for adverse events.

Mindfulness intervention: Based on [name]'s Unified Mindfulness system, lessons train meditation techniques for 3 mindfulness skills: (1) concentration, a stable attention on present-moment body experiences; (2) sensory clarity, the detection and discrimination of sensory experiences; and (3) equanimity, an attitude of acceptance and receptivity toward present-moment experiences. Practice prompts build on the skills trained in each lesson, encouraging participants to practice brief moments of mindful awareness, mindfulness while doing daily tasks, or formal meditation for 5-10 minutes.

Coping control intervention: To parallel the structure of the mindfulness intervention without training present-moment attention or acceptance skills, participants are instructed to: (1) reflect and mind wander; (2) reappraise past and future events; and (3) analyze and solve personal problems. Practice prompts encourage participants to take brief mind-wandering breaks, apply reappraisal or problem-solving skills, or reflect for 5-10 minutes. This program controls for nonspecific effects (e.g., goals, daily practice, and treatment expectancies). Here, an active control program will inform the feasibility of the RCT design for future trials and will preempt differential dropout issues that are commonly seen in studies using no-treatment control groups.

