1. *Ambulatory Stress Assessments*, delivered to participants' smartphones at T1, T3, and T5, will assess (1) EMA stress (state stress perceptions, stress events) and resilience (state positive/negative affect, social interactions) four times daily during between 8am and 8pm, and (2) average daily life stress via diary (stress perceptions, stress events), resilience (positive/negative emotions, social interactions), and intervention practice (T3, T5 only). At T2, participants will complete stress surveys before and after each intervention lesson, before and after each JIT prompt, and each evening, which will inform adherence and JIT prompt timing.
2. *Ambulatory Physiology*, tracked and stored via Fitbit wearable device throughout T1-T5, will include continuous HR data (via photoplethysmography) to pair with EMA stress surveys. Physiological data and continuous physical activity (via pedometer) and sleep (via actigraphy) data will be integrated daily into the AWARE database and will be used in machine learning analyses with passive sensor data to evaluate predictive models of state stress in daily life.
3. *Smartphone Passive Sensor Data* will be collected throughout T1-T5. The open-source AWARE application will be installed on participants' Android or iOS smartphones to continuously and unobtrusively collect data characterizing behavioral and contextual features. Sensor data will include device usage, location, movement, activity, noise, conversation, and communication; these features will be used to predict stress.
4. *Inflammatory biomarkers* will be quantified in batch from DBS samples collected at T1, T3, and T5. Pro-inflammatory cytokine IL-6 will be assessed using R&D's Ella Automated Immunoassay System. A larger panel of pro- and anti-inflammatory markers (e.g., TNF, CRP, IL-8, IL-10) will be assessed via multiplex with additional funding.

Eligibility Criteria:

Inclusion Criteria:

1. Emerging adults between 18 and 29 years old
2. English speaking
3. History of adverse childhood experiences (specifically, moderate-to-severe physical, emotional, or sexual abuse in childhood: scoring >9, >12, or >7 on respective

Childhood Trauma Questionnaire subscales 1)

4. Data-enabled Android or iOS smartphone
5. Able to meet study requirements

Exclusion Criteria:

1. Self-reported diagnosis of chronic physical disease (e.g., cancer, HIV, heart disease, diabetes, bleeding disorder)

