2. Self-reported diagnosis of chronic mental disorder (e.g., schizophrenia, personality disorder, or psychotic illness) major neurological disorder, or suicidal thoughts or wishes at baseline
3. Medication use that interferes with HPA-axis activity (e.g., corticosteroids) or autonomic activity (e.g., antihypertensive medication)
4. Current antibiotic, antiviral, or antimicrobial treatment
5. Shift workers
6. Pregnancy or breastfeeding
7. Excessive alcohol use
8. Frequent illicit drug use
9. Regular systematic mind-body practice (>2 times per week)

Statistical Analysis Plan (SAP)

Power:

Sample size balances rules of thumb for pilot trial sample size (which range from 25-35 participants per treatment arm estimating a small between-group effect size, with larger pilot trials more accurately estimating variance and allowing for smaller sample sizes in efficacy trials) with calculations to detect medium within-group effects of mindfulness on EMA stress ($d=.40$). Therefore, we plan to enroll 80 participants (40 per condition).

Statistical Analysis Plan:

This study will evaluate two primary aims and one exploratory aim:

Aim 1 evaluates the feasibility and acceptability of the interventions and assessments, with the prediction that interventions and assessments will meet feasibility and acceptability benchmarks in this ELA sample, and mindfulness and control groups will show equivalence on these measures.

- Planned analysis: Feasibility and acceptability will be evaluated by comparing screening and enrollment numbers, participant retention, adherence to intervention and assessment protocols, treatment expectancies, intervention fatigue, and prompt timing to proposed benchmarks for success. Specifically, minimum feasibility benchmark ranges are as follows: 10% of those screened will be eligible; 60-70% of eligible participants will enroll; <10% of participants will show increases in daily stress, a measure of safe implementation; 80-90% of enrolled participants will be retained through the intervention period and 75-85% through the follow-up assessment period; participants will complete 85-95% of the intervention lessons, 60-70% of practice prompts, 75-90% of ambulatory assessments, and provide mobile sensor data on >75% of days. ANOVAs will test for equivalence of mindfulness vs. control groups on

feasibility and acceptability outcomes.

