Exploratory aims involve developing machine learning models to estimate daily life stress from passive sensor data and lay the groundwork for future JIT intervention. First, machine learning models developed to estimate daily life stress from passive sensor data aim to have at least 80% accuracy and 70% recall. We will use the open-source RAPIDS pipeline to extract aggregated behavioral features. We will approach stress detection as a binary classification problem where each interval prior to a random EMA is assigned a value of 0 (low stress) or 1 (high stress) based on perceived stress rating and sensor features from that interval are used to predict class membership. We will use the RAPIDS pipeline to evaluate different cross-validation approaches (e.g., leave-one-out) as well as different machine learning algorithms (e.g., random forests, extreme gradient boosting machines). Methods will be evaluated in an iterative and exploratory manner to determine which yields the best performance with regard to accuracy and interpretability. We will examine overall accuracy, precision (i.e., positive predictive value), recall (i.e., sensitivity), and area under the receiver operating characteristic curve (AUROC) in evaluating model performance. Second, MLMs will test whether mindfulness practice prompts delivered at high stress times (operationalized as being ≥ 1 SD above the person-centered stress mean) reduce state stress and end-of-day stress each day during the intervention. These exploratory analyses will inform the design and implementation of a tailored JIT intervention in a future trial.

Finally, analyses will be run separately by sex to examine potential patterns hidden in pooled analyses.

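### A single cut at +1 SD in the exploratory just-in-time prompt analysis gives up information in the graded stress rating and cannot show at what stress level prompts help

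*Combined protocol and SAP*

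**What the plan says.** The second exploratory analysis in the Statistical Analysis Plan uses multilevel models (MLMs) to test whether mindfulness prompts that are "delivered at high stress times (operationalized as being ≥ 1 SD above the person-centered stress mean) reduce state stress and end-of-day stress each day" of the intervention. That is the only definition of high stress given for this analysis. No continuous-stress model, second cut or shape check is named, and no comparison condition is stated.

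The design supplies graded data. Under Procedures, T2, participants are to "receive 3 brief text-based practice prompts daily at random times". Under Measures, Ambulatory Stress Assessments, stress is surveyed at T2 "before and after each JIT prompt, and each evening". The Overview explains that random delivery is meant to allow just-in-time (JIT) prompts to be evaluated retrospectively. The Aim 1 benchmarks expect completion of "60-70% of practice prompts".

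The use of the result is also stated: "These exploratory analyses will inform the design and implementation of a tailored JIT intervention in a future trial".

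**The concern.** Stress at delivery is a graded, person-centred quantity, and random timing lets it vary over its whole range. The plan reduces it to two levels. A prompt at +0.9 SD is classed with one at -2 SD, and a prompt at +1.1 SD with one at +3 SD.

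Two things are at stake. The first is precision: if the benefit of a prompt rises or falls smoothly with stress, a two-level split estimates that pattern less well than the rating itself. The second matters more. Whoever designs a tailored intervention has to decide at what stress level a prompt should be sent. An analysis that presets one level returns a single contrast at that level and cannot say whether a lower or higher one would do better.

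**Working it through.** The documents state no prompt count, precision or power for this analysis, so there is no figure of the plan's own to reproduce.

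**Inputs from the documents**
- 3 prompts a day (Procedures, T2) for 14 days ("T2: Two-week intervention").
- Completion 60-70% and retention through the intervention 80-90% (Aim 1 benchmarks).
- 40 participants per condition (Power). Only mindfulness prompts are named for this analysis.
- Cut at +1 SD (exploratory aims).

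**Assumptions, not in the documents**
- Within-person ratings are near normal unless stated otherwise.
- Completion does not depend on stress level.
- A prompt is usable only if its pre-prompt survey was answered.
- For the efficiency figures, error variance is equal across prompts and there is no between-person variation in slopes.

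**Size of the high-stress group**
- Prompts sent per person: 3 × 14 = 42.
- Completed: 42 × 0.60 = 25.2 to 42 × 0.70 = 29.4.
- Share at or above +1 SD: P(Z ≥ 1) = 0.1587.
- High-stress prompts per person: 25.2 × 0.1587 = 4.0 to 29.4 × 0.1587 = 4.7.
- Across 40 people: 160 to 187. With 32 to 36 retained: 32 × 25.2 × 0.1587 = 128 to 36 × 29.4 × 0.1587 = 168.
- Other rating shapes, per person: 3.0-4.6 with right skew (gamma or lognormal), 5.3-6.2 if uniform, 2.7-10.9 for coarse 5- or 7-point ratings.

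**Information on the slope of benefit against stress**
- Efficiency of the cut relative to the graded rating, for a linear effect, is the squared correlation of Z with the indicator Z ≥ 1: φ(1)² / [p(1 − p)] = 0.2420² / (0.1587 × 0.8413) = 0.439.
- Loss: 1 − 0.439 = 56%. The standard error is larger by 1/√0.439 = 1.51.
- By simulation of other shapes: loss 35-50% with right skew of 0.5 or more, 50% if uniform, 28-64% for coarse ratings.
- In power terms, 80% on the full scale becomes about 46% at a 56% loss, or about 62% at a 35% loss (two-sided 5%, noncentrality multiplied by the square root of the information kept).

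**Information on the average effect above the cut**
- This is closer to the question as the SAP words it. Under normality, the mean of Z given Z ≥ 1 is 0.2420 / 0.1587 = 1.525, and the mean of Z² is 1 + 1.525 = 2.525.
- Using only prompts above the cut, the variance is proportional to 1/0.1587.
- Linear model: variance proportional to 1 + 1.525² = 3.326. Ratio 3.326 × 0.1587 = 0.53, so the cut loses 47%.
- Quadratic model: variance proportional to 1 + 1.525² + (2.525 − 1)²/2 = 4.488. Ratio 4.488 × 0.1587 = 0.71, so the cut loses 29%.

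**If the effect is a step**
- In a simulation with 40 per arm, 42 prompts, 65% completed, residual SD 1, coping-arm prompts as comparator and a step of 0.30 exactly at +1 SD, the cut had 69% power and the linear graded model 37%. The effect size, SD and comparator are assumed.

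**The case against.** The cut can be defended. A JIT trigger either fires or does not, and the first exploratory analysis also treats stress as 0 or 1. The average effect above a candidate trigger answers that question without assuming linearity, and if the truth is a step at +1 SD, the cut wins. The analysis is exploratory, sits in an 80-person feasibility trial, and carries no power claim and no decision rule. The pre-prompt ratings are collected, so a graded model could be fitted later.

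Most of this stands, and it makes the point one of moderate weight. It does not settle where a trigger should sit, and planning the graded model now avoids choosing a threshold after seeing the results.

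Three stronger readings are tempting, and the documents do not support them:
- A reader might infer that the analysis rests on about four prompts per person. That figure describes the high-stress group. If high-stress times are contrasted with other times, the remaining 21-25 completed prompts also contribute, and the MLM pools people. The SAP does not state the comparison, so the figure would be literal only if lower-stress prompts were excluded.
- A reader might infer that more than half the information is lost. The 56% applies to the slope under normality and linearity, and neither is given. Between-person variation in slopes also narrows the gap. In simulations that included it, again with assumed effects and a coping-arm comparator, the powers implied losses of 39-51% for dependence on stress and 22-38% for the effect at high stress.
- A reader might infer that a null result would end the case for tailoring. Nothing in the plan says so.

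**Conclusion.** The concern holds as a limitation of the analysis as specified, not of the data. The firm part depends on no distribution: one preset cut cannot show at what stress level prompts help, although the analysis is meant to guide a tailored design.

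The loss of information is material but illustrative in size. For a smooth effect it is about 56% for the slope under normality and linearity, roughly 35-50% with right-skewed ratings, and about 29-47% for the average effect above the cut under normality. The group of about 4 to 5 high-stress prompts per person also rests on near-normal ratings and on completion that does not vary with stress.

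The calculations treat each prompt as having its own outcome. They do not cover end-of-day stress, where up to three prompts share one evening rating.

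**What to change.** In the exploratory paragraph of the SAP:
- Add to the MLMs the person-centred pre-prompt stress rating as a continuous moderator, in within-person SD units, using all rated prompts and a person-level random slope.
- Include a quadratic or spline term to check the shape.
- Report the estimated prompt effect with 95% CI at 0, +1 and +1.5 SD.
- For end-of-day stress, state how the day's prompt ratings are combined, for example as the mean pre-prompt stress of that day's completed prompts.
- Keep the contrast at ≥ 1 SD alongside as a sensitivity analysis.

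The cost is SAP wording and one re-specified model, with no new data or participants. The downside is that the continuous model assumes a smooth relation and does worse if the true effect is a step at +1 SD. The retained contrast guards against that.

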- Mindfulness training is expected to reduce daily life stress, normalize stress biology, and reduce markers of inflammation from pre-intervention to post-intervention and one-month follow-up.

Exploratory aims involve (1) developing machine learning models to estimate daily life stress from passive sensor data and (2) using these models to inform future JIT intervention.

Methods

Participants:

80 participants will be recruited. English-speaking adults (ages 18-29 years) who report moderate-to-severe physical, emotional, or sexual abuse in childhood (based on Childhood

[figure not shown]
Trauma Questionnaire thresholds) and own data-enabled Android or iOS smartphones will be recruited in Pittsburgh. Those with severe mental health diagnoses (e.g., psychosis) will be excluded for safety. The sample is expected to be 65% white, 30% black, 5% other race; 5% Hispanic; and 50% female.

Recruitment:

Participants will be recruited for a study testing smartphone stress reduction programs, primarily through The University of Pittsburgh Pitt+Me research registry has nearly 30,000 potential participants ages 18-29. Interested participants will be pre-screened online for preliminary eligibility, then invited for an in-person baseline eligibility screening and visit.

Procedures:

Data will be collected across an 8-week study period as follows:

Lab visits include blood draw and questionnaire assessments. Ecological Momentary Assessment (EMA) includes surveys delivered at four random times daily and end-of-day diary assessments. Mobile sensor data collection includes AWARE phone sensor and Fitbit data.

T1: Baseline. Participants will attend a study visit to confirm eligibility, provide informed consent, complete psychosocial assessments, and prepare for the at-home assessments and intervention. Dried blood spot (DBS) samples will be collected to assess inflammatory biomarkers. During a one-week ambulatory stress assessment, participants will provide four ecological momentary assessments (EMA) and one evening diary survey daily assessing stress and resilience; stress physiology (HR) and activity (e.g., steps, sleep) via wearable device; and smartphone sensor data.

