Aim 2 tests for mindfulness intervention changes to establish effect sizes for a future RCT, with the prediction that mindfulness training will reduce daily life stress, normalize stress biology, and reduce markers of inflammation from pre-intervention to post-intervention and one-month follow-up.

- Planned analysis: MLMs will be used to test for mindfulness intervention changes in daily life subjective stress events and perceptions, stress-related HR in daily life (HR during high stress surveys relative to average person-centered HR), and markers of inflammation from pre-intervention to post-intervention and one-month follow-up. Secondary MLM analyses will test for mindfulness intervention changes in daily life resilience (positive/negative affect; social factors) and daily life HRV. Tertiary MLM analyses will test for between-group differences (mindfulness vs. coping intervention) on all outcomes.

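### The by-sex analyses name no between-sex comparison; reporting the sex difference with its 95% CI would serve their purpose better (minor, exploratory)

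*Combined protocol and SAP*

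**What the plan says.** The only commitment on sex-specific analysis is the last sentence of the Statistical Analysis Plan: "analyses will be run separately by sex to examine potential patterns hidden in pooled analyses". It does not say which analyses it covers.

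The Aim 2 planned analysis contains no sex term at any level:
- Primary: "MLMs will be used to test for mindfulness intervention changes in daily life subjective stress events and perceptions", together with stress-related heart rate and inflammation.
- Secondary: "Secondary MLM analyses will test for mindfulness intervention changes in daily life resilience (positive/negative affect; social factors) and daily life HRV".
- Tertiary: "Tertiary MLM analyses will test for between-group differences (mindfulness vs. coping intervention) on all outcomes".

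The exploratory aims add one more multilevel model: "MLMs will test whether mindfulness practice prompts delivered at high stress times" lower stress during the intervention. It too has no sex term. The documents mention no confidence interval for any outcome.

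For the size of the sex-specific cells, Participants expects "5% other race; 5% Hispanic; and 50% female", Power plans 40 per condition, and the Aim 1 benchmarks expect that "80-90% of enrolled participants will be retained through the intervention period and 75-85% through the follow-up assessment period".

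**The concern.** The main kind of pattern that pooling conceals is an intervention effect that differs between women and men. The quantity that describes it is the difference between the two sex-specific effects, with its uncertainty. Fitting the models once in women and once in men does not produce that quantity unless someone takes the further step of comparing the fits, and the SAP does not commit to that step.

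What is at stake is interpretation. With small cells, two samples that share one true effect will often fall on opposite sides of 0.05. If the report shows only two sets of results, a finding significant in one sex alone is easily taken for a sex difference.

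Applying the sentence to the Aim 2 models is my reading. The same reasoning would apply to the practice-prompt model if it is split by sex, but the figures below do not cover that model. The point does not concern the feasibility benchmarks or the machine-learning models.

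**Working it through.** The plan gives no calculation for the by-sex analyses, so there is no figure of its own to reproduce.

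**Inputs from the documents.** 40 per condition and d=0.40 for within-group change in EMA stress (Power); 50% female (Participants); retention of 80-90% through the intervention and 75-85% through follow-up (Aim 1 benchmarks).

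**Assumptions not in the documents.** Two-sided 0.05; d in units of the SD of change; t-tests standing in for the multilevel models; half of each arm female; equal retention by sex and arm; equal SDs; identical true effects in both sexes.

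**Cell sizes per sex per arm.** 40 × 0.50 = 20 at enrolment; 20 × 0.80 to 0.90 = 16-18 post-intervention; 20 × 0.75 to 0.85 = 15-17 at follow-up.

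**Chance that exactly one sex is significant.** If each sex has power p and the sexes are independent, this is 2p(1 − p). At d=0.40:

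| n per cell | p, within mindfulness | one sex only | p, between arms | one sex only |
|---|---|---|---|---|
| 20 | 0.397 | 0.479 | 0.234 | 0.359 |
| 18 | 0.360 | 0.461 | – | – |
| 17 | 0.341 | 0.450 | 0.205 | 0.326 |
| 16 | 0.322 | 0.437 | – | – |
| 15 | 0.303 | 0.423 | 0.185 | 0.301 |

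For example, at n=20 within arm: 2 × 0.397 × 0.603 = 0.479.

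The rate depends on the true effect. Within arm at n=20, p is 0.05, 0.136 and 0.924 at d = 0, 0.2 and 0.8, giving 0.095, 0.235 and 0.141. With equal cells, 2p(1 − p) peaks at 0.50 when p = 0.5, so d=0.40 lies near the peak.

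**What the sex difference would show in those cases.** By simulation (50,000 runs per setting), the share of one-sex-only results in which the 95% CI for the within-arm sex difference includes zero is:

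| n per cell | d=0 | d=0.2 | d=0.40 |
|---|---|---|---|
| 20 | 0.680 | 0.828 | 0.901 |
| 17 | 0.685 | 0.819 | 0.893 |
| 15 | 0.669 | 0.811 | 0.892 |

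Over all runs the interval excludes zero in 4.9-5.2%, as it should.

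**Precision of the sex difference, in SD-of-change units.** Half-width within arm is t(2n−2) × sqrt(2/n); for sex-by-arm it is t(4n−4) × sqrt(4/n).

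| n per cell | within arm: half-width | difference for 80% power | power for 0.40 SD | sex-by-arm: half-width | difference for 80% power | power for 0.40 SD |
|---|---|---|---|---|---|---|
| 20 | 0.640 | 0.909 | 0.234 | 0.891 | 1.269 | 0.143 |
| 17 | 0.699 | 0.991 | 0.205 | 0.969 | 1.380 | 0.128 |
| 15 | 0.748 | 1.060 | 0.185 | 1.034 | 1.472 | 0.119 |

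**Chance findings.** I count eight Aim 2 outcomes: stress events, stress perceptions, stress-related HR, IL-6, positive affect, negative affect, social factors and HRV. IL-6 stands alone for inflammation because "Pro-inflammatory cytokine IL-6 will be assessed using" a named assay, while the wider panel depends on additional funding. Treating outcomes as independent, at least one unadjusted 95% CI excludes zero by chance with probability 1 − 0.95^8 = 0.34 for a single contrast. Two later time points and two models give 4 × 8 = 32 contrasts, and 1 − 0.95^32 = 0.81. These contrasts are correlated, so that figure is only a rough guide.

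**The case against.** The strongest reply is that nothing here is an error. Women and men are independent samples, separate fits are legitimate, and nothing in the SAP prevents their estimates from being reported with standard errors and compared. The lack of confidence intervals is not specific to sex. This is a short pilot SAP with a one-sentence exploratory look. All of that stands, and it keeps the point minor.

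The size of the illustration can also be challenged. It uses t-tests, covers one reading of the sentence, and d=0.40 is given for EMA stress only, with no statement of how it is standardised. If it is in raw-SD units, the 20-per-sex figure becomes 42% at an assumed pre-post correlation of 0.3 and 36% at 0.8. Unequal cells can push it up: an assumed 28/12 split gives 52%. So 42-48% is an indication, and 50% is a ceiling only for equal cells.

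Three stronger readings are tempting, and the documents do not support them:
- *The between-sex difference is the only quantity the stated purpose needs.* Pooling can also mask an effect common to both sexes, for instance if the sexes differ in outcome level and are unbalanced across arms. No stratification by sex is stated. In that case the sex-specific estimates are themselves informative. This bears mainly on the between-arm models.
- *The SAP will declare sex differences by comparing p-values.* It sets no such rule; the risk lies in how results are read.
- *Sex-specific estimates will shape the future trial.* Aim 2 is meant to supply effect sizes for it, but the SAP does not say this of the by-sex results.

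**Conclusion.** The point holds as a modest improvement. The SAP gives a purpose for the by-sex analyses but omits the comparison that would best serve it. With equal true effects of d=0.40 and 15-20 per sex in the mindfulness arm, results significant in one sex only would arise in about 42-48% of outcomes (30-36% for between-arm contrasts), and about nine in ten of the within-arm ones would come with an interval for the sex difference that includes zero. These figures rest on the assumptions listed and fall well below this when the true effect is near zero or large.

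The remedy does not make the pilot able to confirm a moderate sex difference. Within arm, power for a 0.40 SD difference is 19-23% and 80% power needs about 0.91-1.06 SD; for sex-by-arm the figures are 12-14% and 1.27-1.47 SD. No primary conclusion depends on this point.

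**What to change.** Replace the last sentence of the SAP with a short paragraph that does the following:

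1. States which analyses are examined by sex.
2. For the Aim 2 models so examined, reports the between-sex difference in effect with its 95% CI. One route is to add sex-by-time to the within-mindfulness model and sex-by-group-by-time to the between-group model, with lower-order terms. The other keeps the separate runs and subtracts the two estimates, with SE = sqrt(SE1² + SE2²). Subtraction avoids assuming variance components common to both sexes, which a pooled interaction model usually does.
3. Bases any statement about sex differences on that interval.
4. Keeps the sex-specific estimates with CIs as exploratory description, and says they are not adjusted for multiple outcomes.
5. States the limits: only very large sex differences are detectable, a wide interval is not evidence that the sexes respond alike, and chance findings are likely across outcomes, time points and models.

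The cost is SAP wording and a few model terms. With T1, T3 and T5 as categories, the within-mindfulness model gains 3 parameters (1 for sex, 2 for sex-by-time) and the between-group model 6 (1 for sex, 1 for sex-by-group, 2 for sex-by-time, 2 for the three-way term). Subtraction needs no new terms. Neither route needs new data.
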